#### **4.3.3 Subject Disposition**

Study completion status and reasons for discontinuation will be summarized by frequencies and percentages.

#### **4.3.4 Study Product Exposure**

The number of days of exposure will be summarized by the number of non-missing observations, mean, standard deviation, median, minimum, and maximum.

### **5.0 Data Handling Conventions**

This section contains the data handling conventions that will be used to carry out the statistical analyses.

#### **5.1 Baseline and Follow-Up Visits**

Visits and timepoints for all analyses will be as record on the eCRFs. Baseline will be the later of the non-missing values from the Screening and Baseline/Day 1 visits scheduled to occur prior to receiving study medication.

#### **5.2 Missing Data**

Data will be handled on an observed case basis with no imputation..

#### **5.3 Unscheduled Data**

Unscheduled data will not be used in the summaries, but will be presented in the listings.

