7.3.2 Study Procedures by Visit

Visits following the Baseline Visit are to occur at Months 1, 3, 6, 9, and 12 at Week 4, 12, 26, 39 and 52 (Final Visit). Interim study visits and the Final Month 12 (Week 52) study visit may be conducted (on an individual subject basis) up to 14 days before or after the regularly scheduled study visit. An unscheduled visit may occur in the event that the investigator determines that the subject should be seen for safety reasons.

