7.6.10 Safety Summaries

Adverse events will be categorized by SOC and Preferred Term from the current version of MedDRA. The focus of the adverse event summaries will be on treatment-emergent adverse events. Treatment-emergent adverse events will be summarized overall, by severity, and by relationship to study product.

Changes or shifts in safety laboratory data and vital signs will be summarized at all time-points when available. Summaries will include means, standard deviations, median, minimum and maximum values for continuous data, or frequency and percent for categorical data. Additionally, shift tables will be provided for abnormal safety labs.

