##### **4.3.2 Safety Summaries**

The IGA will be summarized across the study duration in order to evaluate safety as it pertains to the underlying condition of papulopustular rosacea.

Adverse events will be categorized by SOC and Preferred Term from the current version of MedDRA. The focus of the adverse event summaries will be on treatment-emergent adverse events. Treatment-emergent adverse events will be summarized overall, by severity, and by relationship to study product.

Changes in safety laboratory data, vital signs, and physical exam will be summarized at all time-points when available. Summaries will include means, standard deviations, median, minimum and maximum values for continuous data, or frequency and percent for categorical data. Additionally, shift tables will be provided for abnormal safety labs.

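### SAP 5.3 sends all unscheduled safety values to listings only; by-visit tables should stay that way, but the lab shift tables should be able to use them (minor, cheap to fix)

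*SAP*

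**What the plan says.** The rule in SAP 5.3 is one sentence: "Unscheduled data will not be used in the summaries, but will be presented in the listings". Neither document qualifies it with a worst-value rule, an any-time table or an exemption for adverse events.

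Protocol 7.3.2 gives one reason for such visits: "An unscheduled visit may occur in the event that the investigator determines that the subject should be seen for safety reasons". The procedures table (Protocol 7.3.1) puts unscheduled visits in the same column as the interim visits. In that column the IGA and adverse event assessment are marked, vital signs are marked for Month 6 only, and clinical laboratory tests are not marked.

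Four other SAP statements bear on the point:

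- SAP 5.1 on visit assignment: "Visits and timepoints for all analyses will be as record on the eCRFs". An unscheduled visit is therefore not mapped to a scheduled one.
- SAP 5.2: "Data will be handled on an observed case basis with no imputation".
- SAP 4.3.2 on labs, vital signs and physical exam: "Changes in safety laboratory data, vital signs, and physical exam will be summarized at all time-points when available". It then adds: "Additionally, shift tables will be provided for abnormal safety labs". Protocol 7.6.10 has similar wording.
- SAP 4.3.2 on the IGA: "The IGA will be summarized across the study duration in order to evaluate safety as it pertains to the underlying condition of papulopustular rosacea".

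**The concern.** Long-term safety is the study's only objective, and the plan relies on descriptive summaries instead of tests. By the protocol's own definition, the values that SAP 5.3 keeps out of those summaries come from visits held because of a safety concern. A listing preserves them but gives no count or percentage.

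This matters most where scheduled data are sparse, and labs are the sparsest. An on-treatment abnormality found between Screening and the final visit, and not judged reportable as an adverse event, would not be counted in any table. A subject who never returns for the final lab would contribute nothing to the lab change and shift tables, even if an on-treatment result were on file.

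**Working it through.** The plan states no figure to reproduce. The check is a count of scheduled assessments, followed by a trace of where each kind of unscheduled value can go.

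**1. Scheduled post-baseline assessments for a 12-month completer** (Protocol 7.3.1, 7.3.2, 7.4.3, 7.4.4; visit window ±2 weeks)

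| Measure | Post-baseline times | Count | Longest interval, nominal | With windows |
|---|---|---|---|---|
| Hematology, chemistry | Week 52 | 1 | 52 − 0 = 52 weeks from Day 1 | 52 + 2 = 54 |
| Vital signs | Weeks 26, 52 | 2 | 52 − 26 = 26 weeks | 26 + 2 + 2 = 30 |
| IGA | Weeks 4, 12, 26, 39, 52 | 5 | 26 − 12 = 14 weeks | 14 + 2 + 2 = 18 |

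These intervals are maxima. Early termination, or the sponsor's close-out once the exposure targets are met (Protocol 7.1), brings the final visit forward.

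**2. Where an unscheduled value can appear**

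| Value from an unscheduled visit | Adverse event tables | Lab, vital-sign or IGA tables | Listings |
|---|---|---|---|
| Lab judged clinically significant | Yes (Protocol 7.4.4) | No (SAP 5.3) | Yes |
| Lab or vital sign not reported as an adverse event | No | No (SAP 5.3) | Yes |
| Rosacea worsening attributed to study drug | Yes (Protocol 7.4.7.1) | No (SAP 5.3) | Yes |
| Rosacea worsening attributed to the disease | No (Protocol 7.4.7.1) | No, unless still present at the next scheduled IGA | Yes |

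Rows two and four are the gap. For row four, the rule in Protocol 7.5.9 that a newly started therapy triggers an adverse event record does not help. It covers conditions absent from the medical history, and rosacea is in that history.

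**3. Subjects with no final-visit lab.** Protocol 7.2.3 asks for final-visit procedures in those who leave early, so most should have a final lab. Someone lost to follow-up may not. Under SAP 5.2 nothing is imputed, and under SAP 5.3 an earlier on-treatment result cannot stand in. That subject is therefore absent from the lab change and shift tables.

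**4. Direction of the effect on a lab shift table.** For one test, let *n* subjects have a final lab, of whom *a* are abnormal. Let *c* have a normal final value but an abnormal unscheduled one. Let *m* have only an unscheduled value, of whom *b* are abnormal.

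- Final visit only: *a* / *n*.
- Worst post-baseline value, unscheduled included: (*a* + *b* + *c*) / (*n* + *m*).

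The count cannot fall, since *b* and *c* are at least 0. The percentage usually rises, but it can fall: if *c* = 0 it does so when *b* / *m* is below *a* / *n*. The documents give none of *b*, *c* and *m*, so the size cannot be computed.

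**The case against.** The case for leaving the rule alone has weight. Scheduled-only by-visit tables are standard, because unscheduled values are selected for cause and would distort a visit mean. The SAP does not promise a worst-value shift table; with one scheduled post-baseline lab, the natural reading is Screening to final visit. Labs are not marked at unscheduled visits and vital signs are not planned there, so it is an inference that such values will exist and reach the eCRF. Clinically significant labs are adverse events. What remains for labs is mostly values the investigator judged unimportant. Protocol 7.3.3.1 describes the IGA as informational. The planned summaries of concomitant medications and discontinuation reasons (SAP 4.3.1, 4.3.3) give further partial cover.

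All of this stands, and it is why the point is minor. It does not remove the gap: with one scheduled lab, the final visit is the only on-treatment lab the tables can show.

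Three stronger readings are tempting, and the documents do not support them.

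- *Adverse events found at unscheduled visits are dropped.* SAP 5.3 could be read that way literally. But Protocol 7.4.7.1 requires every adverse event to be recorded with its onset date, and SAP 4.3.2 summarizes treatment-emergent events without reference to visit. The sensible reading is that they are included.
- *SAP 5.3 contradicts SAP 4.3.2 and Protocol 7.6.10.* The protocol says "Changes or shifts in safety laboratory data and vital signs will be summarized at all time-points when available", but that can mean scheduled time-points only. SAP 5.0 introduces Section 5 as the conventions for carrying out the analyses. This is a tension in wording, not a proven conflict.
- *Much IGA worsening would go unseen.* Any such share depends on how long a flare lasts and when it starts. The documents give neither.

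**Conclusion.** The concern holds in limited form, as a cheap improvement of minor severity. SAP 5.3 is sound for by-visit tables. Its defect is that it also closes off any any-time summary, in a safety study with one scheduled post-baseline lab and two post-baseline vital-sign measurements. The loss is confined to lab and vital-sign values not reported as adverse events, and to subjects whose only on-treatment lab is unscheduled. It rests on the assumption that investigators sometimes order such tests and that the results are entered in the eCRF. The number affected is unknown. No inference changes, since nothing is tested, and all values remain in the listings.

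The IGA is a lesser part of the point. Its unscheduled grades are planned data, and a transient rise attributed to the disease would appear in no adverse event or IGA table. Five scheduled post-baseline grades and the IGA's informational status keep this small.

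**What to change.** Replace SAP 5.3 with a short paragraph stating that:

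- (a) by-visit summaries use scheduled visits only;
- (b) lab shift tables, and any counts of vital-sign abnormalities, use the worst post-baseline value, including unscheduled values, with worst defined separately for high and low where both matter;
- (c) adverse event summaries include all treatment-emergent events whatever the type of visit at which they were recorded;
- (d) unscheduled values continue to be listed.

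Footnote the tables in (b) to say that they include for-cause values. Flag any result not analysed by the central laboratory named in Protocol 7.4.4.

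An any-time IGA summary is optional. If one is added, it should compare with an earlier post-baseline grade, because subjects enter at Grade 4, the top of the scale, and change from baseline cannot show worsening. It should also be labelled as including ordinary fluctuation, since Protocol 5.1 describes the disease as relapsing and remitting and the study has no comparator.

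The cost is one SAP paragraph and minor programming, with no new data and no change to study conduct. The downside is that reported abnormality counts may be slightly higher.
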